#### Statistical analysis:

The mean change from Randomization (Week 12) to Week 24 (Weeks 13,14,15,16,18,20, 22 and 24) in each of the YGTSS subscales will be summarized. This endpoint will be analyzed with a Mixed Model for Repeated Measures (MMRM) model using the SAS MIXED procedure with REPEATED statement. The model with an unstructured covariance matrix will include fixed effects for treatment, visit, interaction between treatment and visit, region, age group (0 = children 6-11, 1 = adolescents 12-17, 2=adults >=18) and covariate for week 12 YGTSS subscale score. Visit will include weeks 13,14,15,16,18, 20, 22 and 24. By visit comparisons will be provided. In the event the model does not converge using the unstructured covariance matrix, the methods described in Section 10.2.4 will be tried. The final covariance structure will be documented in the table. All observed endpoint data will be used in this analysis, without imputation.

Summary statistics will be presented along with a full data listing by treatment group.

10.2.24. Mean change from Baseline (Day 1) to Week 24 in the YGTSS subscales (Motor, Vocal, and Impairment) for ecopipam compared to placebo

An exploratory analysis will be performed on the change in each of the YGTSS subscales from Baseline to Week 24 (Weeks 4, 8, 12, 13, 14, 15, 16, 18, 20, 22 and 24).

#### Statistical analysis:

The analysis method for each of the YGTSS subscale scores will be a Mixed Model for Repeated Measures (MMRM) model using the SAS MIXED procedure with REPEATED statement. The model with an unstructured covariance matrix will include fixed effects for treatment, visit, interaction between treatment and visit, region, age group (0 = children 6-11, 1 = adolescents 12-17, 2=adults >=18) and covariate for baseline YGTSS subscale score. Visit will include weeks 4, 8, 12, 13,14,15,16,18,20, 22 and 24. By visit comparisons will be provided. In the event the model does not converge using the unstructured covariance matrix, the methods described in Section 10.2.4 will be tried. The final covariance structure will be documented in the table. All observed endpoint data will be used in this analysis, without imputation.

Summary statistics will be presented along with a full data listing by treatment group.

#### 10.2.25. Sensitivity Analysis

For exploratory endpoints of mean change, the difference in means between treatment arms in change from Randomization (Week 12) to Week 24 or from Baseline (Day 1) to Week 24, a sensitivity analysis may be performed. For the intercurrent events of study treatment discontinuation due to lack of efficacy, treatment related adverse events, death prior to Week 24 and Relapse for subjects with no assessment at

This document is confidential.

SAP text Version: SAP text 3.0 6-Dec-2023

Controlled Document ID: 3903A.02, Effective Date 31-Aug-2020

Week 24, the non-collected data of assessment at Week 24 will be multiply imputed using similar subjects (relevant demographic/baseline characteristics) from the placebo arm.

For example, the exploratory efficacy analysis on change in the YGTSS-TTS from Randomization (Week 12) to week 24 (Weeks 13, 14, 15, 16, 18, 20, 22 and 24) is to use MMRM model using all observed data. This model is appropriate when data are missing at random (MAR). To assess the robustness of the primary efficacy analysis, the following additional sensitivity analyses for missing data will be included for the mITT set:

- 1. Missing at Random (MAR) predictive mean matching multiple imputation method
- 2. Missing Not at Random (MNAR) jump to reference multiple imputation method
- 3. Tipping point under MNAR assumption

Details of sensitivity analysis for missing data and the statistical model are explained below.

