# 10. Efficacy

# 10.1. Primary Efficacy Endpoint and Analysis

The YGTSS is a clinician-rated, multi-dimensional instrument for assessing tic symptoms in children and adults with TD. It includes a semi-structured interview with either caregivers (for subjects <18 years of age) or adult subjects (≥ 18 years of age) and clinical observations that assess tic and tic-related impairment severity over the previous week. Every attempt should be made, per subject, to complete interview by the same caregiver or subject and same rater for all visits.

Both motor and vocal tics are assessed for symptom number, frequency, intensity, complexity, and interference on a 0–5 Likert scale. Scores from each dimension are totaled to reflect the severity of motor tics (range 0–25), vocal tics (range 0–25) and combined tics, or Total Tic Score (-TSS) (range 0–50). A separate tic-related impairment scale, scored from 0 to 50, is also included and calculated for the Global Severity score (-GS).

YGTSS will be assessed at Screening, Baseline and at Weeks 4, 8, 12, 13, 14, 15, 16, 18, 20, 22, 24 and 7 day follow up visit.

The primary efficacy endpoint is time from Randomization to Relapse defined as a loss of ≥ 50% of the improvement experienced on the YGTSS-TTS from Baseline to the last visit in the open-label Stabilization period (Week 12), or initiation of additional medications to treat symptoms of TD, or requirement of hospitalization for worsening symptoms of TD in subjects ≥ 6 and < 18 years during the double-blind R/WD period for ecopipam compared to placebo. Data from subjects who complete or discontinue from the double-blind R/WD period without Relapse will be considered as censored observations. The log rank test will be the primary test of statistical significance. Kaplan-Meier curves will be used to compare the times to relapse between the treatment groups. The hazard ratio and its 95% confidence interval (CI) will be estimated from the Cox proportional hazard model with treatment as a factor. The proportional hazards assumption will be evaluated graphically and analytically, for example by assessing martingale and Schoenfeld residuals and by modeling time-dependent covariates.

The analysis of the primary efficacy endpoint will be performed in the mITT (primary), ITT, and PP populations according to the randomized treatment.

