### 10.1.1. Sensitivity Analysis

To assess the robustness of the primary efficacy analysis, the following sensitivity analysis will be performed for the mITT and the ITT set:

Assume subjects who are lost to follow up or who discontinue the study for reasons other than Relapse or lack of efficacy meet the Relapse criteria. Their last non-missing date on study will be used as the date of Relapse. Relapse rate will be estimated using Kaplan-Meier methods and the difference between treatment arms will be tested using the log rank test. Cox proportional hazard model will be run with treatment as factor.

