# 1) MAR predictive mean matching multiple imputation method

All missing data will be imputed for patients missing data at week 24 using the predictive mean matching multiple imputation method (Heitjan and Little 1991, Schenker and Taylor 1996) for a MAR data assumption using fully conditional specification (FCS) method. The imputation model will include age group at baseline, region, treatment arm, week 12 YGTSS-TTS, and YGTSS-TTS at all visits up to week 24 (Weeks 13, 14, 15, 16, 18, 20, 22 and 24) where the YGTSS is scheduled to be collected. This imputation will be performed using the SAS MI procedure with fcs specification. The resulting complete, imputed datasets will each be analyzed using the same model as the exploratory analysis of mean change model, and the resulting statistics combined using methodology provided by Rubin (1987) and Little and Rubin (2002). The SAS code for the multiple imputation methodology is detailed in the Appendix (Section 16.2).

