#### 2) MNAR jump to reference multiple imputation method

Data will be imputed for patients missing data at week 24 using similar predictive mean matching multiple imputation method. Under a MNAR data assumption, patients will have their missing data at week 24 imputed as if they behaved like placebo treated patients after dropout. Only placebo patients with complete data will be included in the imputation model. The imputation models will include age group at baseline, region, week 12 YGTSS-TTS score, and YGTSS-TTS scores at all visits up to week 24 (Weeks 13, 14, 15, 16, 18, 20, 22 and 24) where the YGTSS is scheduled to be collected. After obtaining complete data sets, the complete data sets will be used in the analysis. The resulting complete, imputed datasets will each be analyzed using the same model as the primary analysis model, and the resulting statistics combined using methodology provided by Rubin (1987) and Little and Rubin (2002). The SAS code for the multiple imputation methodology is detailed in the Appendix (Section 16.3).

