#### 3) Tipping point analysis:

This document is confidential.

SAP text Version: SAP text 3.0 6-Dec-2023

Controlled Document ID: 3903A.02, Effective Date 31-Aug-2020

In the event that statistical significance in favor of ecopipam is determined from the primary analysis, subjects in the ecopipam group with a missing YGTSS-TTS score (change from randomization) will be assigned successively more extreme values, whilst subjects in the placebo group with a missing YGTSS-TSS score (change from randomization) will be assigned successively less extreme values, to find the point at which statistical significance is lost (i.e. the 2-sided P-value becomes greater than 0.05 or significance is in favor of placebo).

Details for tipping point analysis are described below:

- a. For patients that completed the study, intermittent missing data are considered as MAR and will be imputed by predictive mean matching multiple imputation method (Heitjan and Little 1991, Schenker and Taylor 1996). The imputation model will include age group at baseline, region, treatment arm, week 12 TTS score, and TTS scores at all visits up to the imputed visit where the TTS is scheduled to be collected.
- b. For patients who discontinued due to any reason, all missing data will be imputed using the same predictive mean matching multiple imputation method. The imputed values will be adjusted under MNAR assumption:
  - o Patients randomized to ecopipam: the first missing value after patients dropout will be analyzed assuming the unobserved outcome is on average worsened by  $\delta$ 1 (where  $\delta$ 1 = 1 to 10 or estimated treatment effect (MAR model), whichever is higher, in step of 1) compared to the patients who have no missing value;
  - o Patients treated by placebo: the first missing value after patients dropout will be analyzed assuming the unobserved outcome is on average better by  $\delta 2$  (where  $\delta 2 = 1$  to 10 or estimated treatment effect (MAR model), whichever is higher, in step of 1) compared to the patients who have no missing value;

The penalty or reward will not be applied to the values from later time points as these values are penalized or rewarded through condition on previous time points. For each combination of  $(\delta 1, \delta 2)$ , 100 imputed datasets will be obtained.

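### SAP 10.2.25 presents its imputation and tipping-point analyses as checks of the primary analysis, but they test the exploratory mean-change model; the log-rank censoring is stressed only by 10.1.1, which treats both arms alike

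*SAP*

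**What the plan says.** **Primary analysis.** SAP 10.1 defines the primary endpoint as time from randomization to Relapse in subjects aged 6 to under 18. It states "The log rank test will be the primary test of statistical significance" and sets the censoring rule: "Data from subjects who complete or discontinue from the double-blind R/WD period without Relapse will be considered as censored observations". SAP 7.1 adds that loss to follow-up is taken to be unrelated to treatment.

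**Sensitivity analysis of the primary.** SAP 10.1.1 specifies one: "Assume subjects who are lost to follow up or who discontinue the study for reasons other than Relapse or lack of efficacy" have Relapsed, dated at their last date on study. It names no arm, so it applies to both.

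**Missing-data section.** SAP 10.2.25 opens on a different subject: "For exploratory endpoints of mean change, the difference in means between treatment arms in change from Randomization (Week 12) to Week 24". After taking the YGTSS-TTS MMRM as its example, it continues "To assess the robustness of the primary efficacy analysis, the following additional sensitivity analyses for missing data will be included for the mITT set" and lists MAR predictive mean matching, MNAR jump to reference and an MNAR tipping point.

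**Analysis model.** The three items of 10.2.25.1 do not agree:

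- Item 1 (MAR) analyses the imputed data "using the same model as the exploratory analysis of mean change model".
- Item 2 (jump to reference) has them "analyzed using the same model as the primary analysis model".
- Item 3 (tipping point) begins "In the event that statistical significance in favor of ecopipam is determined from the primary analysis", and its step c again names the primary model.
- Appendix 16.4 analyses the tipping-point data with the exploratory mean-change model and gives PROC MIXED code for the change score.

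**The concern.** Read as written, 10.2.25 promises three missing-data checks of the primary result, and none of them can touch it. The primary relies on dropout without Relapse being non-informative. A reader who takes 10.2.25 at its word would credit the log-rank result with MAR, MNAR and tipping-point support that was never produced.

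Item 3 is also an operating rule. Taken literally, the log-rank result decides whether to search for the point at which a different test loses significance. If the log-rank test is significant and the MMRM is not, there is nothing to tip. If the MMRM is significant and the log-rank test is not, no tipping analysis is run.

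**Working it through.** **1. What each analysis acts on**

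| Analysis | Data changed | Model | Can it move the log-rank p-value? |
|---|---|---|---|
| Primary (10.1) | none | log-rank, age 6 to <18 | – |
| 10.1.1 | Relapse status of dropouts, both arms | log-rank, Cox | yes |
| MAR (10.2.25.1 item 1, App. 16.2) | YGTSS-TTS change, Weeks 13–24 | mean-change MMRM | no |
| Jump to reference (item 2, App. 16.3) | same scores | called the primary model; the appendix gives imputation code only | no |
| Tipping point (item 3, App. 16.4) | same scores, shifted in both arms | called the primary model in step c; PROC MIXED on change in the appendix | no |

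Nothing in the SAP re-derives Relapse status or time from imputed scores. The subjects differ too. The MMRM in 10.2.4 has an adult age group, which the primary excludes. Relapsed subjects are withdrawn from blinded medication (Protocol 7.1), and about half of those randomized are expected to Relapse. Many missing late scores will therefore belong to subjects who are already primary events, not to the censored dropouts on whom the primary depends.

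**2. The plan's own figure.** Inputs from SAP 4.3: 49 events, HR 0.4, two-sided 0.05, 65% and 34% Relapse, 49 per arm.

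- Freedman: z = √49 × (1 − 0.4)/(1 + 0.4) − 1.96 = 3.00 − 1.96 = 1.04, so power is 85.1%. The stated 85% reproduces.
- Expected events: 49 × (0.65 + 0.34) = 48.5.
- Implied HR: ln(0.66)/ln(0.35) = 0.396.

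**3. How hard does 10.1.1 press?** 3,000 trials were simulated at 49 per arm.

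- Relapse times are exponential, with weekly hazards −ln(0.35)/12 = 0.0875 (placebo) and −ln(0.66)/12 = 0.0346 (ecopipam), read at Weeks 13–16, 18, 20, 22 and 24.
- Dropout times are uniform over the 12 weeks and independent of Relapse. Dropouts are dated at the last visit attended.
- The test is log-rank at two-sided 0.05. The Monte Carlo standard error is at most √(0.25/3000) = 0.9 points.
- **The dropout rates are assumptions.** The documents give none for the withdrawal period.

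Power, with approximate HR in brackets:

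| Dropout ecopipam / placebo | Primary (censored) | 10.1.1 (both arms) | Ecopipam dropouts only |
|---|---|---|---|
| 5% / 5% | 87% (0.38) | 85% (0.41) | 79% (0.43) |
| 10% / 10% | 88% (0.38) | 81% (0.44) | 67% (0.49) |
| 20% / 20% | 85% (0.38) | 72% (0.49) | 39% (0.61) |
| 20% / 10% | 86% (0.39) | 55% (0.55) | 37% (0.62) |
| 10% / 20% | 87% (0.38) | 91% (0.39) | 65% (0.49) |

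At 10% per arm, an average of 4.2 ecopipam and 3.3 placebo dropouts are censored. Repeat runs, including one with exponential dropout times tested at 0.0492, put the two right-hand columns at 81–83% and 67–69% for 10% per arm. For 20% per arm the ranges were 72–74% and 39–40%.

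**4. Reading the table.** At 10% per arm, 10.1.1 takes 88 − 81 = 7 points of power and the ecopipam-only stress takes 88 − 67 = 21, so 10.1.1 applies about a third of that loss. With more ecopipam dropout (20% / 10%) it takes 86 − 55 = 31 of 86 − 37 = 49 points, about 63%. With more placebo dropout (10% / 20%) it raises power from 87% to 91%.

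**The case against.** **The wording is probably carried over.** Section 10.2.25 sits under the secondary and exploratory endpoints and opens on exploratory mean change. Item 1 and Appendix 16.4 name the mean-change model, and Protocol 13.4.1 lists these methods straight after the mean-change endpoints. A programmer following the appendix would fit the MMRM. This largely stands as to intent. It does not repair item 2, for which no analysis code is given, or the trigger in item 3.

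**10.1.1 is a serious stress.** This stands. A reader might infer that 10.1.1 is no test of informative censoring because the added events cancel. The documents do not support that: Relapse at dropout is a strong departure from non-informative censoring, and with 20% ecopipam and 10% placebo dropout power falls from 86% to 55%. What it lacks is asymmetry between the arms.

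**The design already captures some worsening at dropout.** Discontinuing subjects should complete early-termination procedures, and the YGTSS is scheduled at that visit (Protocol 7.5, Table 3). New TD medication or hospitalization for TD already counts as Relapse. This stands in part, and the simulation omits the early-termination assessment. It gives no help for a subject lost to follow-up without a final visit. Read literally, 10.1.1 also leaves lack-of-efficacy discontinuations out, so those without Relapse stay censored, whereas the simulation converts every dropout.

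**Ecopipam-only counting is a worst case, and nothing promises more.** Both stand. Protocol 13.4.1 makes further sensitivity analyses of the primary optional, and SAP 7.1 allows others. But the planned ITT and PP runs keep the same censoring rule, and time to treatment discontinuation (SAP 10.2.21) counts discontinuations in both arms as an exploratory endpoint.

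**Two further readings to avoid.** A reader might infer that the log-rank test makes no use of YGTSS-TTS. Observed scores define Relapse; only the imputed values never reach it. A reader might also infer that the mismatched trigger would often misfire. The documents give no score profiles from which to estimate how often.

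**Conclusion.** The point holds in this form. SAP 10.2.25 and items 2 and 3 of 10.2.25.1 attribute to the primary analysis three checks that act on imputed YGTSS-TTS change scores, and the tipping search is triggered by a test other than the one it tips. The primary's censoring is stressed by one specified sensitivity analysis, 10.1.1. This is a genuine check, but it is milder than an asymmetric one when dropout is similar and can favour ecopipam when placebo dropout is higher.

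At an assumed 10% dropout per arm, power is about 88% for the primary, 81–83% under 10.1.1 and 67–69% with ecopipam dropouts alone as Relapses. At 20% per arm it is about 85%, 72–74% and 39–40%. These figures rest on the SAP's 65% and 34% Relapse rates, exponential times, independent dropout and no early-termination rating. The last figure of each set is a bound, not a forecast. The labelling error needs none of these assumptions.

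**What to change.** 1. In the 10.2.25 introduction, and in 10.2.25.1 item 2, the opening of item 3 and its step c, replace *primary* with *exploratory (mean change)*. Trigger the tipping search on the Week 24 MMRM p-value.
2. In 10.1.1 add a time-to-event tipping-point analysis. Multiply impute Relapse times for ecopipam subjects censored before Week 24 for non-administrative reasons, with their post-censoring hazard multiplied by an increasing delta (1, 2, 3 and so on, up to Relapse at dropout). Hold placebo at delta = 1, repeat the log-rank test, and report the delta at which p exceeds 0.0492. State the imputation model and the number of imputations in advance.

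The cost is four wording changes and one more analysis on data already collected. It should be settled before unblinding, because a delta scheme chosen afterwards would carry little weight. The downside for the sponsor is that the analysis may show the primary result to depend on a few ecopipam dropouts.

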## 10.2.25.1. Sensitivity analyses for missing data

Details of sensitivity analyses for missing data includes MAR predictive mean matching multiple imputation method, MNAR jump to reference multiple imputation method, and MNAR tipping point analysis are as follows:

# 1) MAR predictive mean matching multiple imputation method

All missing data will be imputed for patients missing data at week 24 using the predictive mean matching multiple imputation method (Heitjan and Little 1991, Schenker and Taylor 1996) for a MAR data assumption using fully conditional specification (FCS) method. The imputation model will include age group at baseline, region, treatment arm, week 12 YGTSS-TTS, and YGTSS-TTS at all visits up to week 24 (Weeks 13, 14, 15, 16, 18, 20, 22 and 24) where the YGTSS is scheduled to be collected. This imputation will be performed using the SAS MI procedure with fcs specification. The resulting complete, imputed datasets will each be analyzed using the same model as the exploratory analysis of mean change model, and the resulting statistics combined using methodology provided by Rubin (1987) and Little and Rubin (2002). The SAS code for the multiple imputation methodology is detailed in the Appendix (Section 16.2).

#### 2) MNAR jump to reference multiple imputation method

Data will be imputed for patients missing data at week 24 using similar predictive mean matching multiple imputation method. Under a MNAR data assumption, patients will have their missing data at week 24 imputed as if they behaved like placebo treated patients after dropout. Only placebo patients with complete data will be included in the imputation model. The imputation models will include age group at baseline, region, week 12 YGTSS-TTS score, and YGTSS-TTS scores at all visits up to week 24 (Weeks 13, 14, 15, 16, 18, 20, 22 and 24) where the YGTSS is scheduled to be collected. After obtaining complete data sets, the complete data sets will be used in the analysis. The resulting complete, imputed datasets will each be analyzed using the same model as the primary analysis model, and the resulting statistics combined using methodology provided by Rubin (1987) and Little and Rubin (2002). The SAS code for the multiple imputation methodology is detailed in the Appendix (Section 16.3).

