# 4.3. Determination of Sample Size

The planned number of Relapse events for the double-blind R/WD Phase is 49 in children and adolescents. This number of events will provide 85% power to detect a difference between treatment groups, assuming a hazard ratio of 0.4 for Relapse and statistical testing at alpha level 0.05 (2-sided). Subject enrollment will stop around the time that 49 Relapse events among children and adolescents are anticipated to have occurred. The number of Relapse events among adults will not determine study completion.

Assuming the proportion of subjects who Relapse in the DB randomization phase is 65% in the placebo group and 34% in the ecopipam group, approximately 98 subjects (49 subjects per group) will be required to achieve this number of Relapse events.

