# 16.3. MNAR jump to reference multiple imputation methodology

The monotone method will be used to impute missing values for TTS of the YGTSS change values and will use age group at baseline, region, and week 12 TTS score to determine the scores (100 imputations will be created). Only placebo patients with complete data will be included in the imputation model.

The SAS code for the imputation is as follows:

```
proc mi data=final out=mi2 seed=123 nimpute=100; class agegrp region arm; monotone reg;

mnar model( _13 /modelobs=( arm='Placebo')); mnar model( _14 /modelobs=( arm='Placebo')); mnar model( _15 /modelobs=( arm='Placebo')); mnar model( _16 /modelobs=( arm='Placebo')); mnar model( _18 /modelobs=( arm='Placebo')); mnar model( _20 /modelobs=( arm='Placebo')); mnar model( _24 /modelobs=( arm='Placebo')); var agegrp region wk12 _13 _14 _15 _16 _18 _20 _22 _24; run;
```

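### The jump-to-reference text imputes from placebo completers only, which selects on outcome, and the code printed for it specifies a different analysis

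*SAP*

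**What the plan says.** Protocol 13.4.1 names jump-to-reference multiple imputation as a possible sensitivity analysis and leaves the detail to the SAP. The SAP specifies it in three places.

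- **SAP 10.2.25.1(2), text.** The aim is to impute as if the subject had followed the placebo course after dropout. Method: "Data will be imputed for patients missing data at week 24 using similar predictive mean matching multiple imputation method". Reference set: "Only placebo patients with complete data will be included in the imputation model". Predictors: age group, region, the Week 12 score and "YGTSS-TTS scores at all visits up to week 24 (Weeks 13, 14, 15, 16, 18, 20, 22 and 24".
- **SAP 16.3, narrative.** It repeats the complete-data restriction, but names only age group, region and the Week 12 score as predictors.
- **SAP 16.3, code.** The method line is "class agegrp region arm; monotone reg". Each MNAR statement filters on the placebo arm, with no completeness condition. The statements cover Weeks 13 to 20 and then go straight to Week 24: "mnar model( _20 /modelobs=( arm='Placebo')); mnar model( _24 /modelobs=( arm='Placebo". Week 22 is nevertheless in the variable list, and treatment arm is not: "var agegrp region wk12 _13 _14 _15 _16 _18 _20 _22 _24".

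Three other provisions matter. SAP 4.1 withdraws relapsed subjects from blinded drug. SAP 8.4 assigns early-termination scores to the next scheduled visit. SAP 10.2.25 expects some relapsed subjects to have no Week 24 assessment. The planning assumption in SAP 4.3 reads: "Assuming the proportion of subjects who Relapse in the DB randomization phase is 65% in the placebo group and 34% in the ecopipam group".

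**The concern.** A jump-to-reference analysis should show what happens if subjects with missing scores behave like the placebo arm from then on. Here the commonest expected reason for a missing Week 24 score is relapse, which is itself defined mainly by the tic score being imputed. Requiring complete data therefore removes from the reference set most of the placebo subjects who got worse. Under predictive mean matching an imputed value can only be a value seen in a donor, so early relapsers receive completers' scores.

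The text, the narrative and the code also cannot all be run. They differ on donors, method and predictors, and the results differ enough that the choice should not be left until after unblinding.

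**Working it through.** **1. The plan's own figures reproduce.** Inputs from SAP 4.3: hazard ratio 0.4, two-sided alpha 0.05, power 85%, relapse 65% and 34%, 49 per group. Freedman's formula gives (1.960 + 1.036)² × (1.4/0.6)² = 8.98 × 5.44 = 48.9, so 49 events. Power at 49 events: 7 × 0.6/1.4 − 1.960 = 1.04, or 85.1%. Expected events in 98 subjects: 49 × 0.65 + 49 × 0.34 = 48.5.

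**2. Size of the reference set, placebo, 49 subjects.**
- Never relapse: 49 × 0.35 = 17.2.
- Not relapsed by Week 22, constant hazard assumed: 0.35^(10/12) = 0.417, or 49 × 0.417 = 20.4. The extra 6.7 percentage points first relapse at Week 24 and still have complete data.
- The documents give no dropout rate. With an assumed 20%, and no first relapses at Week 24: 17.2 × 0.80 = 13.7.
- Range: about 14 to 20 of 49, or 28% to 42%.

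The mean-change models also include adults. If 40 adults enrol, half respond and 10 join each arm, with paediatric relapse rates, the count before dropout is 59 × 0.35 = 20.7 to 59 × 0.417 = 24.6.

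**3. Predictors.** Week 24 is predicted from age group, region, Week 12 and seven later visits. That is 10 variables (11 coefficients with three age groups), of which 8 are scores, fitted to about 14 to 20 paediatric placebo subjects.

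**4. Where the restriction acts.** If scores stop at relapse, the placebo subjects observed at Week 24 are the completers under either donor rule. The restriction changes the models for the earlier visits, where subjects relapsing at that visit would otherwise contribute.

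**5. Simulation A.** 49 per arm, calibrated to 65%/34% relapse. Assumed: baseline mean 33, SD 6; 27-75% improvement at Week 12; visit noise SD 2.2; scores missing after the relapse visit; no other dropout. Predictors were Week 12 and earlier visits. Results are for placebo subjects relapsing before Week 24. Their median rise from Week 12 was 9.7 points at the relapse visit and 11.8 at Week 24 had they been followed.

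| Imputation | Median rise at Week 24 | Below relapse threshold |
|---|---|---|
| True value | 11.8 | 20% |
| Text: matching, placebo completers | 6.6 | 62% |
| Regression, placebo completers | 9.4 | 39% |
| Code as printed | 12.0 | 26% |
| Code with Week 22 restored | 12.1 | 26% |

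With regression throughout, the restriction moves the share from 26% to 39%; matching on so few donors moves it on to 62%. With 500 per arm the four shares are 40%, 37%, 21% and 20%, so the effect of the restriction remains while that of matching largely goes. In the ecopipam arm (49 per arm), early relapsers are imputed at 5.6 points under the text and 9.1 under the code, against 8.7 at their relapse visit.

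**6. Simulation B.** 200,000 per arm, same relapse calibration; its score trajectories are not set out here, so only direction is used. Regression and matching agreed.

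| | Completers only | All observed placebo | True |
|---|---|---|---|
| Placebo mean change | 5.0 | 6.5 | 6.5 |
| Difference, ecopipam − placebo | −2.6 | −3.4 | −3.8 |
| Implied ecopipam mean (sum) | 2.4 | 3.1 | 2.7 |

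Completers-only imputation lowers the placebo mean by 1.5 and the ecopipam mean by 0.7, because more placebo subjects are imputed. The difference shrinks.

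**The case against.** The strongest reply is that little depends on this analysis. SAP 10.2.25 introduces it as one that may be performed, on exploratory mean-change endpoints outside the testing sequence in 10.2. A MAR analysis and a tipping-point analysis stand beside it, and the primary endpoint has its own sensitivity analysis in 10.1.1. All of that stands, although 10.2.25 goes on to say that these analyses will be included.

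The second reply is that the code is sound on the main point, since it has no completeness filter and showed little bias in Simulation A. That stands too, but both the 10.2.25.1(2) text and the 16.3 narrative state the restriction, so the code does not settle it.

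Third, it is not fully settled that relapsers' Week 24 scores are missing. Relapse shares a visit column with Week 24 and early termination, and SAP 8.1 summarises by nominal visit while 8.4 reassigns early-termination scores. The reference to relapsers without a Week 24 assessment supports missingness, but 8.1 and 8.4 need reconciling.

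A reader might go further and infer any of the following, which the documents do not support:
- *The Week 22 gap makes relapsers appear to recover.* Without the statement, and with arm absent from the variable list, Week 22 would be imputed from both arms pooled. That is a separate coding error; restoring the line moved the median from 12.0 to 12.1. Code lines in 16.4 are out of order in the text as read, so the gap should be checked against the program file.
- *Complete subjects are exactly the non-relapsers.* Week 24 relapsers are complete, and dropouts without relapse are not.
- *Imputed relapsers return to their Week 12 state.* Under the text they were still imputed 6.6 points above it in Simulation A. The pull is partial.

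**Conclusion.** The point holds for the method as worded. The complete-data restriction selects on outcome, leaves about 14 to 20 of 49 placebo subjects as the reference, and pulls early relapsers in both arms towards completers' scores. The result cannot be read as a jump to the placebo arm. The bias follows from the text and the 16.3 narrative, not from the printed code, which is a different analysis.

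The direction follows from the donor rule. The sizes rest on assumed trajectories, a constant hazard, an assumed dropout range and a paediatric planning rate. It would be tempting to conclude that the flaw flatters ecopipam; in Simulation B it shrank the difference (−2.6 against −3.4). The analysis is therefore hard to interpret, but not tilted towards the drug on that evidence. The consequence is confined to a sensitivity analysis of exploratory mean-change endpoints.

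**What to change.** In SAP 10.2.25.1(2) and 16.3:

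1. Delete the complete-data restriction. Fit each visit's model on all placebo subjects observed at that visit, including relapse-visit scores placed as in 8.4, and reconcile 8.4 with the nominal-visit rule in 8.1.
2. State one method, regression or predictive mean matching, in text and code. The choice matters: if scores stop at relapse, Week 24 donors under matching are completers even without the restriction, so some of the pull would remain in a trial of this size.
3. State one predictor list in the text, narrative and code. Keep it short enough for the Week 24 model, which stays thin under either donor rule.
4. Add the Week 22 MNAR statement.

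The cost is a few sentences of SAP text and a few lines of SAS, settled before unblinding. No new data are needed.
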